## 7.2 Baseline Testing/Prestudy Evaluation

### Pre-Screening Evaluation

The medical charts for the proposed study eligibility (pre-screen) will be reviewed.

### Screen 1 Visit

Participants who wish to be considered for registration will undergo a screening evaluation. A complete history and physical exam will be obtained at the screening visit. Additionally, labs will be ordered/reviewed to assess eligibility, and imaging will be reviewed to assess cirrhosis.

- Informed Consent
- Medical History
- Record Concomitant Medications
- Physical Exam & Vital Signs
- Ultrasound, CT or MRI of the abdomen will be performed at Screen 1, Screen 2, or at Visit 1 prior to starting agent, if not performed within 3 months prior to consent
- FibroScan will be performed at Screen 1, Screen 2, or at Visit 1 prior to starting agent, if not performed within 3 months prior to consent
- Clinical Labs – including CBC with differential and platelets, comprehensive metabolic panel including BUN, creatinine, sodium, potassium, chloride, calcium, bicarbonate, glucose, liver function tests including AST, ALT alkaline phosphatase, total protein, albumin, direct bilirubin, indirect bilirubin, and total bilirubin, magnesium, GGT, and phosphorous, coagulation test (INR), AFP and AFP-L3.

- Calculate Child Pugh score
- Pregnancy Test (only offered for premenopausal women with child-bearing potential).
- If the participant has archival liver biopsy tissue collected within the last 12 months prior to consent, the archival tissue can be tested (or sent for testing) for  $\gamma$ -OHPdG at either Screen 1 or Screen 2.

Screen 1 Visit will be performed 0-60 days prior to registration. Screen 1 and Screen 2 visit procedures may be combined or split into multiple visits, as long as they occur within the window specified. Participants should not have liver biopsy until after confirmation of Screen 1 clinical blood lab results.

## **Screen 2 Visit**

Participants who meet the Screen 1 eligibility criteria, will return for the Screen 2 Visit.

- Ultrasound, CT or MRI of the abdomen will be performed at Screen 1, Screen 2, or at Visit 1 prior to starting agent, if not performed within 3 months prior to consent
- FibroScan will be performed at Screen 1, Screen 2, or at Visit 1 prior to starting agent, if not performed within 3 months prior to consent
- Liver biopsy is required for participants who have no archival liver biopsy tissue adequate for  $\gamma$ -OHPdG testing collected and stored within 12 months prior to consent. Participants with archival liver biopsy tissue adequate for  $\gamma$ -OHPdG testing and collected and stored within 12 months prior to consent, may optionally have the liver biopsy at Screen 2.
- If the participant has archival liver biopsy tissue collected within 12 months prior to consent, the archival tissue can be tested (or sent for testing) for  $\gamma$ -OHPdG at either Screen 1 or Screen 2.
- Research Urine for  $\gamma$ -OHPdG level
- The liver biopsy samples will be tested for  $\gamma$ -OHPdG level, if this was not done previously
- The pathology slides will be reviewed and scored for the  $\gamma$ -OHPdG level by pathologists.

Screen 2 Visit will be performed 0-60 days prior to registration. Screen 1 and Screen 2 visit procedures may be combined or split into multiple visits, as long as they occur within the window specified. Participants should not have liver biopsy until after confirmation of Screen 1 clinical blood lab results.

## **Registration and Randomization**

Participants will be registered between Screen 2 and Visit 1 (week 1 day 1). For more information, see protocol section 6.8 Registration. There is no randomization in this study.

### **7.3 Evaluation During Study Intervention**

#### **Study Visit 1 (Week 1 Day 1)**

Participants will come to the clinic to receive study procedures and their first dose of study agent. Participants who volunteer for the PK tests at Georgetown will be asked to fast after midnight except for drinking water prior to coming into the clinic.

- Ultrasound, CT or MRI of the abdomen will be performed at Screen 1, Screen 2, or at Visit 1 prior to starting agent, if not performed within 3 months prior to consent
- FibroScan will be performed at Screen 1, Screen 2, or at Visit 1 prior to starting agent, if

- not performed within 3 months prior to consent
- If the participant is pre-menopausal and of child-bearing potential, and has not had a negative pregnancy test within 72 hours prior to starting study agent, another pregnancy test will be performed at this visit. If a test is performed, the result must be negative in order to start agent.
- Record Concomitant Medications
- Physical Exam & Vital Signs
- Adverse Events Assessments.
- Venipuncture for clinical labs
- Clinical Labs – including CBC with differential and platelets, comprehensive metabolic panel including BUN, creatinine, sodium, potassium, chloride, calcium, bicarbonate, glucose, liver function tests including AST, ALT alkaline phosphatase, total protein, albumin, direct bilirubin, indirect bilirubin, and total bilirubin, magnesium, GGT, and phosphorous, coagulation test (INR), AFP and AFP-L3.
- Administer the Alcohol and Tobacco Baseline Assessments (Appendices E & F)
- Provide participant with the participant diary (Appendix C), agent study drug instructions (Appendix B), and the resources handout (Appendix I).
- Research Blood (for  $\gamma$ -OHPdG level)
- Research Blood PKs (for the first six participants at Georgetown University who agree)
- Research Urine PKs (for the first six participants at Georgetown University who agree)
- Research Urine for  $\gamma$ -OHPdG level if participant had archival biopsy
- Dispensation of study drug

Study Visit 1 will be performed 0-14 days after registration.

### Between Visits 1 and 2

Participants will complete weekly or bi-weekly liver function & coagulation tests according to the chart below. These tests can be done with local lab or MD, for convenience; LabCorp or Quest are preferred, as the results will be reported directly to hospital electronic medical chart. If another lab is used, the report can be requested to be faxed to the investigator and/or study coordinator.

- Venipuncture for clinical labs
- Liver function tests, including ALT, AST, direct bilirubin, indirect bilirubin, and total bilirubin, alkaline phosphatase, total protein, albumin, GGT, calcium, phosphorous, and magnesium
- Coagulation test (INR)

| Assigned Dose  | Schedule of liver function & coagulation tests  |
|--|---|
| 400 mg EGCG QD or
400 mg EGCG BID   | Bi-weekly liver function & coagulation testing (every 14 +/- 3 days)  |
| $\geq$ 600 mg EGCG BID   | Weekly liver function & coagulation testing (every 7 +/- 3 days) for the first 2 weeks on agent, or until the participant demonstrates stability of clinical condition and liver biochemical enzymes* for at least 2 weeks, whichever is longer. Thereafter, the participant will receive bi-weekly liver function & coagulation testing (every 14 +/- 3 days). |
| * Stability of clinical condition and liver biochemical enzymes is defined as meeting all of the following, as listed in Appendix D: |   |

- a. No symptoms of clinical hepatitis (vomiting, nausea, right upper quadrant pain)
- b. No ALT or AST increases to  $\geq 5$ x upper limit of normal
- c. No ALT or AST increases to  $\geq 3$ x baseline levels
- d. No elevations in direct bilirubin  $> 1.5 \times$  ULN.
- e. No elevation of direct bilirubin  $>$  ULN, regardless of ALT or AST levels, with indicators of immunological reaction (i.e., rash or  $> 5\%$  eosinophilia).

### Study Visit 2 (Week 13 +/-3 days)

After taking the study medication for 12 weeks +/-3 days, participants will return to the clinic.

- Record Concomitant Medications
- Physical Exam & Vital Signs
- Adverse Events Assessments.
- Venipuncture for clinical labs
- Clinical Labs – including CBC with differential and platelets, comprehensive metabolic panel including BUN, creatinine, sodium, potassium, chloride, calcium, bicarbonate, glucose, liver function tests including AST, ALT alkaline phosphatase, total protein, albumin, direct bilirubin, indirect bilirubin, total bilirubin, magnesium, GGT, and phosphorous, coagulation test (INR), AFP and AFP-L3.
- Research Urine collection (compliance)
- Research Blood collection (for  $\gamma$ -OHPdG level)
- Dispensation of study drug
- Participant diary review and unused pill count
- Give participant blank participant diary

### Between Visits 2 and 3

Participants will complete weekly or bi-weekly liver function & coagulation tests according to the chart below. These tests can be done with local lab or MD, for convenience; LabCorp or Quest are preferred, as the results will be reported directly to hospital electronic medical chart. If another lab is used, the report can be requested to be faxed to the investigator and/or study coordinator.

- Venipuncture for clinical labs
- Liver function tests, including ALT, AST, direct bilirubin, indirect bilirubin, total bilirubin, alkaline phosphatase, total protein, albumin, GGT, calcium, phosphorous, and magnesium
- Coagulation test (INR)

| Assigned Dose                        | Schedule of liver function & coagulation tests   |
|--------------------------------------|--|
| 400 mg EGCG QD or
400 mg EGCG BID | Bi-weekly liver function & coagulation testing (every 14 +/- 3 days)   |
| $\geq 600$ mg EGCG BID               | 
If the participant has previously demonstrated stability of clinical condition and liver biochemical enzymes* for at least 2 weeks, the participant will receive bi-weekly liver function & coagulation testing (every 14 +/- 3 days).
 
If the participant has not already demonstrated stability of clinical condition and liver biochemical enzymes* for at least 2 weeks, the participant will receive weekly liver function & coagulation testing
 |

|   |   |
|---|---|
|   | (every 7 +/- 3 days) until the participant demonstrates stability* for at least 2 weeks. Thereafter, the participant will receive bi-weekly liver function & coagulation testing (every 14 +/- 3 days). |
| 
* Stability of clinical condition and liver biochemical enzymes is defined as meeting all of the following, as listed in Appendix D:
 

a. No symptoms of clinical hepatitis (vomiting, nausea, right upper quadrant pain)

b. No ALT or AST increases to <math>\geq 5</math>x upper limit of normal

c. No ALT or AST increases to <math>\geq 3</math>x baseline levels

d. No elevations in direct bilirubin <math>> 1.5 \times</math> ULN.

e. No elevation of direct bilirubin <math>></math> ULN, regardless of ALT or AST levels, with indicators of immunological reaction (i.e., rash or <math>> 5\%</math> eosinophilia).

 |   |

## 7.4 Evaluation at Completion of Study Intervention

### Study Visit 3 (Week 25 +/- 3 days)

After their last day of taking the study agent, the participant will come in for a clinic visit.

- Record Concomitant Medications
- Physical Exam & Vital Signs
- Adverse Events Assessments.
- Administer the Alcohol and Tobacco Follow-up Questionnaire (Appendices G & H)
- Venipuncture for clinical labs
- Clinical Labs – including CBC with differential and platelets, comprehensive metabolic panel including BUN, creatinine, sodium, potassium, chloride, calcium, bicarbonate, glucose, liver function tests including AST, ALT alkaline phosphatase, total protein, albumin, direct bilirubin, indirect bilirubin, total bilirubin, magnesium, GGT, and phosphorous, coagulation test (INR), AFP and AFP-L3.
- Research Urine Collection (compliance)
- Research Blood collection (for  $\gamma$ -OHPdG level)
- Calculate Child Pugh score
- Participant diary review and unused pill count
- Ultrasound, CT or MRI of the abdomen (this procedure can be performed at a separate visit  $\pm 3$  weeks from the Visit 3 date). The same imaging performed during screening should be performed at Study Visit 3.
- FibroScan (this procedure can be performed at a separate visit  $\pm 3$  weeks from the Visit 3 date).
- Liver biopsy

## 7.5 Post-intervention Follow-up Period/ Final Evaluations, Off Study

### Study Visit 4 (Week 28 +/- 3 days)

After a 3 week follow-up, participants will return to the clinic.

- Physical Exam & Vital Signs
- Venipuncture for clinical labs
- Clinical Labs – including CBC with differential and platelets, comprehensive metabolic panel including BUN, creatinine, sodium, potassium, chloride, calcium, bicarbonate, glucose, liver function tests including AST, ALT alkaline phosphatase, total protein,

albumin, direct bilirubin, indirect bilirubin, and total bilirubin, magnesium, GGT, and phosphorous, coagulation test (INR), AFP and AFP-L3.

## 7.6 Methods for Clinical Procedures

### **Informed Consent**

The Investigator must obtain documented consent from each potential subject prior to participating in this clinical trial. Consent must be documented by the subject's dated signature or by the subject's legally acceptable representative's dated signature on a consent form along with the dated signature of the person conducting the consent discussion. A copy of the signed and dated consent form should be given to the subject before participation in the trial. The initial informed consent form, any subsequent revised written informed consent form, and any written information provided to the subject must receive the IRB/ERC's approval/favorable opinion in advance of use. The subject or his/her legally acceptable representative should be informed in a timely manner if new information becomes available that may be relevant to the subject's willingness to continue participation in the trial. The communication of this information will be provided and documented via a revised consent form or addendum to the original consent form that captures the subject's dated signature or by the subject's legally acceptable representative's dated signature. Specifics about the trial and trial population will be added to the consent form template at the protocol level. The informed consent will adhere to IRB/ERC requirements, applicable laws and regulations, and Sponsor requirements.

### **Inclusion/Exclusion Criteria**

All inclusion and exclusion criteria will be reviewed by a study physician to ensure that the subject qualifies for the trial. See protocol section 6.8 Registration/Randomization for more information.

### **Medical History and physical exam (H&P)**

A medical history will be obtained by the investigator or qualified designee. Medical history will include all active conditions, and any condition diagnosed within the prior 10 years that are considered to be clinically significant by the Investigator.

Information collected in the H&P is as follows:

1. All prescription, herbal medications, vitamins, and supplements taken, starting at Screen 1 or 28 days prior to starting study agent, whichever is earlier. Any medication or vaccine (including over-the-counter or prescription medicines, vitamins and/or herbal supplements) that the subject is receiving at Screen 1 up to the Final Visit must be recorded in source documents and the case report forms (CRFs). The reason for use, date(s) of administration (including start and end dates), and dosage information (including dose and frequency) must be recorded. Any change in concomitant therapy during the study period must be similarly recorded. Questions regarding prior or concomitant therapy should be directed to one of the investigators.
2. Vital signs including history of weight change.
3. Complete physical exam.
4. Laboratory study results must be obtained within 60 days prior to registration include the following:
  - Complete blood count (CBC) with differential and platelets.

- Serum chemistries:
  - Complete Metabolic Panel including BUN, creatinine, sodium, potassium, chloride, calcium, bicarbonate, glucose
  - Liver function tests including AST, ALT, alkaline phosphatase, total protein, albumin, direct bilirubin, indirect bilirubin, total bilirubin, magnesium, GGT, calcium, and phosphorus.
  - Coagulation test (INR)
  - Tumor marker- AFP, AFP-L3.
- For women of child bearing potential, a serum  $\beta$ -HCG pregnancy test. This is for premenopausal women are those who have had the last menstrual period (LMP) within the last 12 months OR those who have had a hysterectomy, but have at least one intact ovary and are under age 55. Premenopausal women with child-bearing potential are those with at least one ovary, an intact uterus, and LMP less than 12 months previously
- Radiographic evaluation of cirrhosis or development of HCC with FibroScan and either ultrasound, CT or MRI.

### **Prior Medications Review**

The investigator or qualified designee will review prior medication use, including any protocol-specified washout requirement, and record prior medication taken by the subject starting at Screen 1 or within 28 days before starting study agent, whichever is earlier. Treatment for the disease for which the subject has registered in this study will be recorded separately and not listed as a prior medication.

### **Concomitant Medications Review**

The investigator or qualified designee will record medication, if any, that will be taken by the subject during the trial. All medications related to reportable SAEs and ECIs should be recorded as defined.

### **Disease Details and Treatments**

The investigator or qualified designee will obtain prior and current details regarding disease status, and review all prior treatments including those for HBV and HCV.

### **Assignment of Screening Number**

All participant records and tissue specimens will be de-identified using a letter and number assigned to their case at the time of screening. Screening ID blocks will be provided by Northwestern, and assigned to the participant by the accrual site at the time of screening. No record or specimen will contain information that could identify the participant. The key that connects participant identifiable information with this assigned number will be held by the Principal investigator. For computer records, the key will be protected by a double password protection system. Any paper records will be contained in a locked cabinet within a locked office to ensure participants' privacy is protected.

### **Biopsies**

Of note, participants who are on chronic anticoagulation will be required to hold anticoagulation prior to the biopsies being performed. Participants on warfarin must hold treatment for 5 days, but will be on low-molecular weight heparin (LMWH), 1 mg/kg subcutaneously twice a day. LMWH

will continue until the evening prior to the biopsy. LMWH will be held in the morning of the procedure, but the patient will receive LMWH the evening of the day of biopsy. Participant may then resume warfarin the day of biopsy.

Preferred biopsy is core biopsy; 14 -18 gauge (G), 2.11-1.27 mm outer diameter (OD), 1.6-0.84 mm inner diameter (ID), 0.254-0.216 mm wall thickness, hypodermic needles can be used to perform the core biopsies based on the sites standard of care procedures. The use of a 16G needle is highly recommended as it is the most appropriate size to use for percutaneous liver biopsies (70,71). Twenty (20) unstained liver biopsy sections, cut 4-microns-thick must be submitted to the [name] laboratory at Georgetown University/Lombardi for assessment of  $\gamma$ -OHPdG levels in liver samples. Subjects with high levels of  $\gamma$ -OHPdG (IHC stain  $=/ > 3$ ) who meet all other eligibility criteria will then be receive Polyphenon E treatment. A random liver biopsy will be performed at 24 weeks (+/- 7 days) prior to end of treatment. The liver tissue will be evaluated by [name] laboratory at Georgetown University/Lombardi to assess for  $\gamma$ -OHPdG levels (Section 10.2). Liver biopsy samples will be stored in the lab of [name].  $\gamma$ -OHPdG testing of the liver biopsy will be carried out at least twice each month at [name] lab. The liver biopsy samples will be shipped Monday-Thursday, after communication with the receiving site.

Lastly, all liver biopsies taken during the course of the study, regardless of the indication (i.e., both protocol-defined and those performed for other clinical indications) must be assessed by the PIs and the pathologists at Georgetown University Hospital.

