**Dose Escalation Schema**

Discontinue Therapy Criteria (DTC):

- a. Grade 3 or higher toxicity based on CTCAE criteria which is possibly, probably, or definitely related to the study agent OR
- b. Requires discontinuation of treatment based on the Hepatotoxicity Assessment Algorithm (Appendix D) OR
- c. Any hepatic decompensation such as
  1. New onset ascites or worsening of ascites (requiring increase in drug therapy or requiring surgical intervention such as paracentesis).
  2. Variceal bleeding documented by endoscopy
  3. Spontaneous bacterial peritonitis documented by positive culture
  4. Hepatic encephalopathy
  5. Hepatorenal syndrome (Type 1 or 2)
  6. Porto-pulmonary hypertension
  7. Hepato-pulmonary hypertension
  8. Any liver related event that leads to hospitalization or G4 event.

One month following the end of intervention (i.e. 7 months from study entry), subjects will have a post-therapy clinic visit, to be evaluated for the resolution of any side effect from the treatment and review of the six-month repeat scan results. All participants will have a repeat liver biopsy (exit biopsy) taken at the end of the 24 week intervention (see **Participant Flow Schema** at the beginning of this document). The Participant Flow Schema at the beginning of this document summarizes the sequence of events for participants. Details are not presented in the Schema, but can be found under Section 7.

In our unpublished data, 68 participants with cirrhosis, 38% (90% confidence interval, range 0.28, 0.49) of cirrhotic liver biopsies demonstrated high  $\gamma$ -OHPdG levels (IHC score  $\geq 3$ ). Therefore, a minimum of 4 and maximum of 171 participants with liver cirrhosis will be screened in our current study. A minimum of 2 and a maximum of 48 participants whose cirrhotic liver biopsies show a  $\gamma$ -OHPdG score  $\geq 3$  will be enrolled. If a maximum tolerated dose is established, a total of 24 participants will receive the maximum tolerated dose.

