## 4. PARTICIPANT SELECTION

### 4.1 Inclusion Criteria

4.1.1 Participants with a clinical diagnosis of cirrhosis based on the investigators evaluation, confirmed by ANY ONE of the three following methods to define cirrhosis:

- Established cirrhosis on liver biopsy (METAVIR F4);
- Ultrasound, CT or MRI findings consistent with cirrhosis. Nodular appearing liver with or without evidence of portal hypertension

- Transient elastography (FibroScan) with a result  $> 12.5$  kPa  
Etiology of cirrhosis will not be considered in determining inclusion in the study.

4.1.2 Participant is able and willing to comply with study procedures, and signed and dated informed consent is obtained.

4.1.3 Participant agrees to consume no more than 2 cups of green tea per day and refrain from taking supplements or foods labeled as containing green tea.

4.1.4 Participant must be aged  $\geq 18$  years. Because no dosing or adverse event (AE) data are currently available on the use of Polyphenon E in participants  $< 18$  years of age, children are excluded from this study but will be eligible for future pediatric trials, if applicable.

4.1.5 ECOG performance status  $\leq 1$  (Karnofsky  $\geq 70\%$ ; see Appendix A).

4.1.6 Participants must have adequate organ and marrow function as defined below in Table 2:

Table 2:

| System  | Laboratory Value  |
|---|---|
| Hematological  |   |
| Platelets   | $\geq 75,000 / \mu\text{L}$   |
| Hemoglobin  | $\geq 8 \text{ g/dL}$   |
| Renal function   |   |
| Serum creatinine OR
Measured or calculated a creatinine clearance
(GFR can also be used in place of creatinine or CrCl) | Within normal institutional limits OR
GFR within normal institutional limits as adjusted for age and sex. |
| Hepatic function   |   |
| Serum direct bilirubin  | Within normal institutional limits  |
| AST (SGOT) and ALT (SGPT)   | $\leq 2.5 \times \text{UNL}$  |
| Albumin   | $\geq 3.0 \text{ g/dL}$   |
| Coagulation  |   |
| International Normalized Ratio (INR)  | $\leq 1.3$  |
| Other  |   |
| Ascites   | Absent  |
| Encephalopathy  | Absent  |

4.1.7 Only participants found to express high levels (IHC score 3 and above) of  $\gamma$ -OHPdG ( $\gamma$ -OHPdG-high HCC) in baseline or archival liver biopsy will be registered to receive Polyphenon E treatment.

4.1.8 Participant is able to undergo radiographic evaluation with ultrasound, CT or MRI.

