## **5.7 Adherence/Compliance**

5.7.1 All toxicity and samples from all subjects who receive drug will be evaluated and included in the primary analysis, which will be based on intent to treat principle.

5.7.2 The unused pill count and/or participant diary will be provided to and collected from participants by the study coordinator every 3 months during clinic visits for the 6 months of Polyphenon E treatment.

5.7.3 Additionally, an adequate record of receipt, distribution, and return of all study drugs must be kept in a pill count form for the pharmacist to complete.

5.7.4 Measuring the three major metabolites (EGCG, EGC, and EC) of green tea catechins in urine will provide additional evidence of compliance. Pill count and diary are usually used for compliance, however these parameters could be misreported or tampered by participants. For this purpose, urine samples will be collected at Visit 2 and Visit 3.

Subject compliance with the treatment and protocol includes willingness to comply with all aspects of the protocol, and to have blood collected for all safety evaluations. At the discretion of the principal investigator, a subject may be discontinued from the trial for non-compliance with follow-up visits or study drug.

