### **8.3 Off-Agent Criteria**

Participants may stop taking study agent for the following reasons: completed the protocol-prescribed intervention, AE or serious adverse event (SAE) (see section 5.6, Appendix D), inadequate agent supply, noncompliance, concomitant medications, or medical contraindication. Participants will continue to be followed, if possible, for safety reasons and in order to collect endpoint data according to the 7.1 SCHEDULE OF EVENTS.

For any non-liver related toxicities, Polyphenon E will be held for grade 2 adverse events attributed by the treatment until the adverse reaction resolves or improves to baseline, at which time Polyphenon E can be re-initiated at the same dose level. If the adverse reaction re-occurs at grade 2, Polyphenon E should be permanently discontinued.

Hepatotoxicity Assessment Algorithm (**Appendix D**) is being used for hepatotoxicity safety monitoring, in conjunction with NCI CTCAE which is used for grading of adverse events. We will monitor participants' laboratory parameters every 1-2 weeks as recommended, according to protocol section 7. Regarding hepatotoxicity, the procedures for laboratory monitoring, treatment interruption, preinitiation, or permanent discontinuation are described in detail in Appendix D.

If the participant meets at least one criterion of Appendix D, but close monitoring of a participant is not possible, the participant will be taken off agent.

If the participant meets any Discontinue Therapy Criteria, the participant will be taken off agent. DTC is defined as:

- a. Grade 3 or higher toxicity based on CTCAE criteria which is possibly, probably, or definitely related to the study agent OR
- b. Requires discontinuation of treatment based on the Hepatotoxicity Assessment Algorithm (Appendix D) OR
- c. Any hepatic decompensation such as
  1. New onset ascites or worsening of ascites (requiring increase in drug therapy or requiring surgical intervention such as paracentesis).
  2. Variceal bleeding documented by endoscopy
  3. Spontaneous bacterial peritonitis documented by positive culture
  4. Hepatic encephalopathy
  5. Hepatorenal syndrome (Type 1 or 2)
  6. Porto-pulmonary hypertension
  7. Hepato-pulmonary hypertension
  8. Any liver related event that leads to hospitalization or G4 event.

Participants taken off-agent due to adverse event will be followed until resolution of the adverse event or until stabilization of labs and the participant's clinical picture.

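### The exit biopsy is timed both before and after the last dose, with no limit on the off-drug interval, so early stoppers' tissue can be pooled as post-treatment in the primary biomarker analysis

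*Combined protocol and SAP*

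**What the plan says.** The change in liver γ-OHPdG between the baseline and exit biopsies is one of the two primary objectives (sections 1.1.2 and 13.4). The plan times the exit biopsy in several ways:

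- Section 7.6, Biopsies: "A random liver biopsy will be performed at 24 weeks (+/- 7 days) prior to end of treatment".
- Section 7.4 lists it among the Visit 3 procedures (week 25 ± 3 days) and opens with "After their last day of taking the study agent, the participant will come in for a clinic visit".
- Section 3.1: "All participants will have a repeat liver biopsy (exit biopsy) taken at the end of the 24 week intervention".
- Section 8.1.2 also places it at the end of intervention, section 10.2 and the schedule of events at Visit 3, and section 2.5.3 six months after treatment starts.

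No section says which wording governs or sets a maximum interval from last dose to biopsy.

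For participants who come off agent, section 8.3 states: "Participants will continue to be followed, if possible, for safety reasons and in order to collect endpoint data", following the schedule of events. Sections 5.7.1 and 13.8 include all samples from everyone who received drug in the primary analysis, on the intent-to-treat principle.

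Section 5.7.4 adds a urinary catechin check because pill counts and diaries can be misreported: "For this purpose, urine samples will be collected at Visit 2 and Visit 3".

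**The concern.** A before-after comparison has a clear meaning only if the second sample is taken at a known point relative to exposure. Here one section takes it on drug, another takes it off drug, and participants who stopped early are biopsied on the same calendar as those who did not. All of these samples count as post-treatment, and no analysis in section 13 uses time since last dose.

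If the adduct recovers after the drug is stopped, off-drug pairs pull the estimated suppression toward zero. They could also distort the dose trend if they cluster in one cohort. In a trial that closed with 10 pairs, a reader could not tell a weak drug effect from a late biopsy.

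**Working it through.** **1. Day windows.** Inputs: 24 weeks of dosing (section 5.1), the Visit 3 window (section 7.4) and the biopsy window (section 7.6). The week convention comes from Visit 2, headed week 13: "After taking the study medication for 12 weeks +/-3 days, participants will return to the clinic". Week 25 therefore begins after 24 weeks.

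- Planned last dose: 24 × 7 = day 168.
- Visit 3: 168 + 1 = day 169, ± 3 gives days 166 to 172.
- Section 7.6: 168 ± 7 gives days 161 to 175.

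The section 7.6 window contains the whole Visit 3 window. It also conflicts with its own wording, since days 169 to 175 are not before the end of a 24-week treatment.

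**2. On-schedule gaps, last dose on day 168.** A section 7.6 biopsy can fall up to 168 − 161 = 7 days before the end of dosing. A Visit 3 biopsy on days 169 to 172 falls 1 to 4 days after it.

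**3. Early-stopper gaps.** With the exit biopsy at nominal Visit 3 (day 169), a participant whose last dose is at the end of week 12 (day 84) is 169 − 84 = 85 days off drug. One who stops at the end of week 4 (day 28) is 169 − 28 = 141 days off drug. Section 13.6 bases the main analysis on complete data, and such a pair is complete, so it stays in.

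**4. The plan's power.** Section 13.4 gives 0.84466 and 0.94694 for N = 24, SD 2 and mean differences of 1.33 and 1.60. Take a one-sample noncentral t with the Wilcoxon efficiency factor 3/π: 24 × 3/π = 22.9, rounded down to 22. The noncentralities are 0.665 × √22 = 3.12 and 0.80 × √22 = 3.75, and the powers are 0.84466 and 0.94694, an exact match. The calculation gives every pair the full effect. With the 10 pairs obtained (effective n = 10 × 3/π), the same method gives about 0.45 and 0.59, whatever the biopsy timing.

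**5. Possible dilution (assumed rates).** The documents give no recovery rate for hepatic γ-OHPdG. For an assumed recovery half-time h, the share of suppression lost after g days off drug is 1 − 0.5^(g/h):

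| Assumed h (days) | g = 1 | g = 4 | g = 85 |
|---|---|---|---|
| 3 | 21% | 60% | about 100% |
| 7 | 9% | 33% | about 100% |
| 14 | 5% | 18% | 99% |
| 30 | 2% | 9% | 86% |

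If a fraction m of pairs loses a share r of the effect, the mean change becomes 1.33 × (1 − m·r). One fully recovered pair in 10 gives 1.33 × (1 − 0.1) = 1.20.

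**6. Where a pair would matter most.** In Table 6, Cohort 4 has 4 starters, 2 pairs and the only event meeting the Discontinue Therapy Criteria. Section 8.3 takes such a participant off agent. The documents do not say whether that participant supplied one of the 2 pairs. If so, half of the top cohort's biomarker data in the dose-trend test would be off drug.

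**7. Visit 3 urine.** With the last dose on day 168, a sample on days 169 to 172 is 1 to 4 days after it. The plan's own catechin sampling runs to 8.5 h in blood and at most 24 h in urine (section 3.2).

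**The case against.** The strongest reply is that the conflict is mostly wording. Sections 3.1, 8.1.2, 10.2 and the schedule of events agree on Visit 3 or end of intervention, section 7.6 is the outlier, and the windows overlap. Even the four-day gap is not established: Visit 3 opens on day 166 yet is meant to follow the last dose, so the last dosing day may move with the visit, and section 7.6 supplies an extra week of capsules. This stands. For completers the difference is days after 24 weeks of exposure.

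A second reply is that including early stoppers is the declared intent-to-treat choice. That also stands, and the primary analysis should stay as it is. It does not remove the need to show how much of the tissue was on drug.

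A reader might infer that the primary biomarker does mix on-drug and off-drug livers. The documents only permit it. Three of the 13 treated participants have no pair, and nothing shows that any early stopper had an exit biopsy. Nor do the documents support a rapid rebound. Their only time course (section 2.5.1: 65% suppression at 16 weeks and 83% at 32 weeks with Theaphenon E) comes from repair-deficient mice still on treatment, so it says nothing direct about recovery after stopping.

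A reader might also infer that the Visit 3 urine will mislabel adherent participants, or that permitted green tea will imitate capsules. The documents give no catechin half-life or assay detection limit, and the only catechin content quoted for a tea drink comes from a study of a high-density catechin tea. Urine is supporting evidence beside pill count and diary, Visit 2 urine is taken on drug, and no planned analysis depends on compliance.

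**Conclusion.** The concern holds in limited form. Sections 7.6 and 7.4 contradict each other on whether the primary-endpoint tissue is taken before or after the last dose, and no interval is set. For participants who complete dosing, the resulting spread is a matter of days. For early stoppers, sections 8.3, 5.7.1 and 13.8 together allow tissue weeks or months off drug to count as post-treatment.

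The size of any effect on the result is unknown. It depends on whether any early stopper is among the 10 pairs and on how fast the adduct recovers, and the documents state neither. The dilution figures above rest on assumed recovery times and on the plan's effect of 1.33. They show that early stopping matters far more than the wording conflict, not that bias occurred. The stated power is reproduced and is not itself an error. The Visit 3 urine is a weaker adherence check than Visit 2, with no consequence for a planned analysis.

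**What to change.** 1. Reconcile sections 2.5.3, 3.1, 7.4, 7.6, 8.1.2 and 10.2 to one biopsy timing, stated relative to the last dose. Which timing it is remains for the sponsor and investigators to decide.
2. Derive the interval from last dose to exit biopsy from the diary, checked against the pill count, and list it beside each of the 10 before-after pairs.
3. Keep the intent-to-treat analysis as primary. Add a sensitivity analysis of the IHC comparison and the LC-MS dose trend that excludes pairs biopsied more than a pre-set interval after the last dose, fixed before intervals are matched to biomarker values. A cut-off such as 7 days would remove no on-schedule Visit 3 pair (the largest such gap is 4 days), so it isolates early stoppers. The listing covers the shorter gaps.
4. Report the last-dose-to-collection interval with the Visit 3 compliance urine, and rely mainly on Visit 2 urine for chemical compliance.

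The cost is wording changes, one derived variable and one sensitivity analysis on data already collected. If any pair is excluded, that analysis rests on fewer than 10 pairs and can only be descriptive. The last-dose date also comes from a diary that section 5.7.4 accepts may be misreported.
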